9.0 Sample collection and storage for future correlative studies

Tissue samples will be collected and stored as below, at baseline, Day 14 (+7) of Cycle 1, and at the time of surgery for biomarker analysis including ER and Ki67 and for future correlative studies. In addition, blood will be collected for serum, plasma, and germ-line and cell free DNA and stored at baseline for future correlative studies. The correlative studies will be performed in collaboration with [name] at the Siteman Cancer Center and [name] and [name] at the City of Hope Comprehensive Cancer Center.

Sample Collection/Shipment Kit

The kit is a two-chamber kit in which it is possible to ship both frozen and ambient specimens. The kit is stocked with necessary items needed for blood and tumor sample collection. It also contains the necessary materials used to process and prepare specimens for shipment in accordance to IATA regulations.

Washington University Tissue Procurement Core Facility (WUTPC)
[name]
[name]
[contact]
Email: [contact]

Sample collection/shipment kits are available for institutions by sending the request to Email: [contact] with the subject "FELINE Trial Biopsy Kit Request".

9.1 Required pre-treatment core biopsy for biomarker and correlative studies:

Samples collection is mandatory for all patients prior to initiating study therapy.

Core biopsy should be performed with image guidance using a 14 gauge needle. The required biopsies include two core biopsies placed in 10% buffered formalin (a single pre-filled formalin container to hold both cores) and two core biopsies frozen **immediately at bedside** in separate OCT blocks. The cryo kits, formalin containing cup and blood collection tubes will be provided in the sample collection/shipment kits to the sites and are funded by this study.

Tissue may be obtained concurrent with another procedure (clip placement, axillary node biopsy, port placement) or as a separate procedure.

9.2 Required Day 14 (+7) core biopsy for biomarker and correlative studies:

One 10mL lavender top EDTA vacutainer tube (for plasma and buffy coat cell pellet), 1 8.5mL red/black marble top tube (for serum) and 2 10mL Streck BCT tubes (for cell free plasma DNA) will be collected. Sample processing for serum, plasma, and viable buffy coat sections are performed at the participating site and stored at -80°C before shipment. Streck BCT tube blood is not processed but shipped ambient overnight via the specimen collection/shipment kits with all other samples to the Washington University Tissue Procurement Core Facility (WUTPC) for further processing to cell free plasma.

All samples will be appropriately labeled (study number, subject number and date of collection) before being stored. These samples are going to be used in future studies to assess biomarkers such as tumor markers, cell free tumor DNA, SNPs, genetic changes, etc.

If a subject withdraws from the main study participation and future use of specimens is withdrawn by the subject (submitted in writing to the investigator), best efforts will be made to stop any ongoing studies and to destroy the specimens.

All specimens are to be processed and stored in the WUTPC for a period of 20 years or until used up for future research.

Upon the approval of the study PI, de-identified blood specimens may be shared with potential research collaborators outside of the University of Kansas for biomarker work related only to the hypothesis of this study. Collaborators will be required to complete an agreement (Material Transfer Agreement or recharge agreement) that states specimens will only be released for use in disclosed research. Any data obtained from the use of clinical specimen will be the property of the University of Kansas for publication and any licensing agreement will be strictly enforced.

The following information may be provided to research collaborators when specimens are made available:

- Diagnosis
- Collection time in relation to study treatment
- Clinical outcome – if available
- Demographic data (which does not include any protected health information)

The specimens, DNA, and their derivatives may have significant therapeutic or commercial value. The Informed Consent form contains this information and informs the subject that there is the potential for financial gain by the University of Kansas, the investigator or a collaborating researcher or entity.

9.5 Shipping instructions for all research samples (tissue and blood):

The Washington University Tissue Procurement Core Facility (WUTPC) will store the research samples. The formalin fixed cores in the formalin cup received from the shipment will be further processed for tumor Ki67 at the CLIA certified Anatomic and Molecular Pathology Core Labs (AMP) at Barnes Jewish Hospital at St. Louis (CLIA number 26D2013203). Slides and blocks from AMP will be returned to WU TPC for storage after completion of analysis and reporting.

Specimens collected and preserved from outside sites will be shipped overnight (may use the two-chamber kit to ship both frozen specimens (OCT embedded frozen tumor biopsy cores, serum, plasma and cell pellet) on dry ice and ambient specimens (formalin cup with biopsy cores). A completed shipping manifest will be completed, emailed to the Wash U TPC (Email: [contact]), and included in the specimen shipment.

Arrange for Federal Express pick-up through your usual institutional procedure. Ship specimens to the address below:

Washington University Tissue Procurement Core
[name]
[name]
[contact]
E-mail: [contact]

On the day that specimens are sent to the specimen bank, please contact the bank by phone, fax, or e-mail to notify what is being sent and when the shipment is expected to arrive.

9.6 Tissue Processing and Ki67:

9.6.1 Baseline and Day 14 (+7d)

Upon receipt of the specimen, the 2 fixed biopsy specimens at baseline and 2-week will be further processed for tumor Ki67 analysis at the CLIA certified Anatomic and Molecular Pathology Core Labs at Barnes Jewish Hospital at St. Louis (CLIA number 26D2013203). After embedding in paraffin, one section from the tumor block will be stained with H&E to assess biopsy adequacy. Another section from the block will be incubated with antibody against Ki67 (clone 30-9) and then assayed using the Ventana Benchmark platform. The block and any remaining sections will be returned to the Tissue Procurement Core Facility at the completion of testing. Both cores will be reviewed and will be taken into account for the scoring.

Ki67 scoring is reported as a quantitative/continuously distributed value. The Ki67 data for Day 14 biopsy is available real time to the treating physician and the patients. Patients will be continued on protocol therapy while awaiting analysis results. Results of tumor Ki67 will be reported within 10 working days upon receipt of the samples. Wash U Coordinator will email and fax the results to both the CRA listed on Specimen Submission CRF that is sent with the tissue samples and Wash U CRA. Contact Wash U coordinator for questions related to the Ki67 result.

Note: If the biopsy yielded no tumor cells, the patient may continue on study drug therapy or proceed with a second biopsy for Ki67 determination.

9.6.2 Surgery

Ki67 on surgical specimen will be performed on one of the 10 unstained slides cut at 4 microns thickness from tumor rich block obtained after breast surgery.

The 2 fixed biopsy cores obtained at surgery time point will be further processed to FFPE core at the CLIA certified Anatomic and Molecular Pathology Core Labs at Barnes Jewish Hospital at St. Louis (CLIA number 26D2013203). After embedding in paraffin, the block will be stored at the Wash U TPC unless Ki67 could not be obtained on the surgical slides, in which case, further sectioning and staining for Ki67 will be performed.

9.7 Correlative studies: See Appendix E.

10.0 Measurement of Effect

10.1 Response Criteria:

10.1.1 Clinical responses will be based on the WHO criteria

Prior to each cycle of neoadjuvant treatment and at the completion of neoadjuvant treatment, the longest axis and the perpendicular axis of the measurable lesion should be measured and recorded in metric notation by bi-dimensional tape, ruler or caliper technique.

Complete Response (CR) is defined as the disappearance of all known disease based on a comparison between the pre-treatment measurements and the measurements taken at the completion of neoadjuvant therapy (that is, at the end of cycle 6 neoadjuvant endocrine therapy). In addition, there is no appearance of new lesions.

Partial Response (PR) is defined as a 50% or greater decrease in the product of the bi-dimensional measurements of the lesion (total tumor size) between the clinical pre-treatment measurements and the clinical measurements taken at the completion of neoadjuvant therapy. In addition, there can be no appearance of new lesions or progression of any lesion.

No Change (NC) occurs when a 50% decrease in total tumor size cannot be established, nor has a 25% increase in the size of the lesion been demonstrated.

10.2 Definition of pathologic response and events during follow up:

- A pathologic complete response is defined as no histology evidence of invasive tumor cells in the surgical breast specimen and sentinel or axillary lymph nodes.
- Following surgery, diagnosis of breast cancer recurrence and other cancer events:

- Local recurrence - Local recurrence is defined as histologic evidence of ductal carcinoma in situ or invasive breast cancer in the ipsilateral breast or chest wall.
- Regional recurrence - Regional recurrence is defined as the cytologic or histologic evidence of disease in the ipsilateral internal mammary, ipsilateral supraclavicular, ipsilateral infraclavicular and/or ipsilateral axillary nodes or soft tissue of the ipsilateral axilla.
- Distant recurrence - Distant recurrence is defined as the cytologic, histologic, and/or radiographic evidence of disease in the skin, subcutaneous tissue, lymph nodes (other than local or regional metastasis), lung, bone marrow, central nervous system or histologic and/or radiographic evidence of skeletal or liver metastasis.
- Second primary breast cancer - Second primary breast cancer is defined as histologic evidence of ductal carcinoma in situ or invasive breast cancer in the contralateral breast or chest wall.
- Second primary cancer (non-breast) - Any non-breast second primary cancer other than squamous or basal cell carcinoma of the skin, melanoma in situ, or carcinoma in situ of the cervix is to be reported and should be confirmed histologically whenever possible.
- Death - Underlying cause of death is to be reported.

10.3 Safety/Tolerability

Analyses will be performed for all subjects having received at least one dose of study drug. The study will use the CTCAE version 4.03 (<http://ctep.cancer.gov/reporting/ctc.html>) for reporting of adverse events.

10.4 Central MRI Assessment

Radiographic disease response will be assessed by centralized, blinded group of Breast Radiology experts at KUCC. MRI images performed at baseline and Cycle 3 will be submitted to KUCC. The blinded radiology team will perform an independent review of the MRI images.

11.0 DATA AND SAFETY MONITORING

11.1 Oversight and Monitoring Plan:

The DSMC of the KUCC is responsible for monitoring subject safety for this trial. The DSMC is responsible for:

- Review of all clinical trials conducted by the KUCC for progress and safety
- Review of all adverse events requiring expedited reporting as defined in the protocol
- Submission of recommendations for corrective action to the PI and the Deputy Director of the KUCC or designee.
- Notification of external sites participating in multiple-institutional clinical trials coordinated by the KUCC of adverse events requiring expedited reporting and subsequent committee recommendations for study modifications.

11.2 Review and Oversight Requirements:

a) Serious Adverse Event

Serious adverse events that require expedited reporting will be reviewed by the DSMC Chair or designee who will determine if immediate action is required. Refer to Section 7.2. If determined

to be necessary by the DSMC, all participating sites will be notified of the event and any resulting action within one working day of this determination.

b) Review of Serious Adverse Event Rates

Once per month, serious adverse event rates will be monitored by the DSMC Coordinator. If any study has had 2 or more of the same SAE reported within one month, or more than 6 of the same SAE in 6 months, the DSMC will review summaries of SAEs, and discuss events in detail with the PI. The DSMC chair or designee determines whether further action is required. The DSMC Coordinator ensures that collaborating investigators and IRBs for all Participating sites are notified of any resulting action.

c) Study Safety and Progress

The multidisciplinary KUCC Data and Safety Monitoring Committee (DSMC) is charged with overseeing the monitoring of participant safety, conduct and scientific progress of research protocols, and the validity and integrity of the data for clinical trials. The KUCC DSMC has the authority to require amendments, suspend, or terminate any research activities that fall within its jurisdiction, and can institute other appropriate actions as needed to protect participant safety.

The study will be monitored at appropriate intervals, no less than those assigned by the KUCC Protocol Review and Monitoring Committee, to assure compliance to GCP and to assess the data quality and study integrity. The frequency of monitoring may vary depending on enrollment rate and the quality of data collected.

The investigator and staff are expected to cooperate and provide all relevant study documentation in detail at each site visit on request for review. The study monitor will have direct access to source data for data verification. Data verification will be conducted by comparing the data entered into the CRFs with source data

12.0 REGULATORY CONSIDERATIONS

12.1 Protocol Review and Amendments:

This protocol, the proposed informed consent and all forms of participant information related to the study (e.g., advertisements used to recruit participants) and any other necessary documents must be submitted, reviewed and approved by a properly constituted IRB governing each study location.

Any changes made to the protocol must be submitted as amendments and must be approved by the IRB prior to implementation. Any changes in study conduct must be reported to the IRB. The Principal Investigator will disseminate protocol amendment information to all participating investigators.

All decisions of the IRB concerning the conduct of the study must be made in writing.

12.2 Informed Consent:

All participants must be provided a consent form describing this study and providing sufficient information for participants to make an informed decision about their participation in this study. The formal consent of a participant, using the IRB approved consent form, must be obtained before the participant is involved in any study-related procedure. The consent form must be signed and dated by the participant or the participant's legally authorized representative, and by the person obtaining the consent. The participant must be given a copy of the signed and dated

consent document. The original signed copy of the consent document must be retained in the medical record or research file.

12.3 Ethics and Good Clinical Practice (GCP):

This study is to be conducted according to the following considerations, which represent good and sound research practice:

1. ICH Consolidated Good Clinical Practice: Guidelines (E6)
www.fda.gov/cder/guidance/iche6.htm
2. US Code of Federal Regulations (CFR) governing clinical study conduct and ethical principles that have their origin in the Declaration of Helsinki
 - Title 21 Part 11 – Electronic Records; Electronic Signatures
www.access.gpo.gov/nara/cfr/waisidx_02/21cfr11_02.html
 - Title 21 Part 50 – Protection of Human Patients
www.access.gpo.gov/nara/cfr/waisidx_02/21cfr50_02.html
 - Title 21 Part 54 – Financial Disclosure by Clinical Investigators
www.access.gpo.gov/nara/cfr/waisidx_02/21cfr54_02.html
 - Title 21 Part 56 – Institutional Review Boards
www.access.gpo.gov/nara/cfr/waisidx_02/21cfr56_02.html
 - Title 21 Part 312 – Investigational New Drug Application
www.access.gpo.gov/nara/cfr/waisidx_02/21cfr312_02.html
3. State laws
4. Institutional research policies and procedures
<http://www2.kumc.edu/researchcompliance/hscpolicies.htm>

It is understood that deviations from the protocol should be avoided, except when necessary to eliminate an immediate hazard to a research participant. In such case, the deviation must be reported to the IRB according to the local reporting policy.

13.0 REGISTRATION PROCEDURES

13.1 General Guidelines for KUCC and Other Participating Organizations:

Institutions will register eligible subjects through the KUCC Clinical Research Office central registration process. Registration must occur prior to the initiation of therapy. Any subject not registered to the protocol before treatment begins will be considered ineligible and registration will be denied.

The completed source documentation provided for eligibility verification and registration must be kept in the subject binder for monitoring purposes and documentation of subject eligibility.

Issues that would cause treatment delays should be discussed with the Principal Investigator. If a subject does not receive protocol therapy following registration, notify the KU Cancer Center Project Director or designee and change the subject's status in the eVELOS system.

13.2 Registration Process for KUCC and Other Participating Centers:

The Coordinating Center (KUCC), specifically the Project Director or designee is accessible for registration Monday through Friday from 8:00 AM to 5:00 PM Central Time.

The registration procedures are as follows:

1. Obtain written informed consent from the subject prior to the performance of any study related procedures or assessments.
2. Complete the appropriate baseline demographic information in eVELOS and the required registration form and inclusion/exclusion criteria checklist using the eligibility assessment documented in the subject's medical/research record. To be eligible for registration to the study, the subject must meet each inclusion and none of the exclusion criteria listed in Section 3.0 of this protocol. The KU department of biostatistics will grant access to eVelos for this study for access to study documents, patient enrollment and data entry into eCRFs.
3. Submit the registration form and inclusion/exclusion criteria checklist to KUMC via email. The KU Project Director or designee will send an email confirmation stating whether or not the subject may enroll.
4. The unblinded pharmacist or designee will assign the subject to a treatment group using sequential assignment of predetermined block randomized 1:1:1 treatment assignments provided by the study statistician prior to activation.

13.3 Unblinding:

Due to the objectives of the study, treatment assignments will not be known to investigators, research staff, or participants. The study blind will be broken on completion of the clinical study and after the study database has been locked.

During the study, the blind may be broken **only** in medical emergencies when knowledge of the participant's treatment group is necessary for further patient management. When possible, the investigator should discuss the emergency with the Sponsor-Investigator prior to unblinding.

If the decision is made to unblind a participant's treatment in a medical emergency, the following steps should be taken:

1. Contact the investigational pharmacy to request unblinding of the participant, providing the pharmacist with the rationale for unblinding.
2. Document the date, time, and reason for the unblinding. This documentation should be archived in the Investigator Site File, the participant's medical records, and in the eCRF.
3. Notify the Sponsor-Investigator and DSMC of the unblinding event.

If a serious adverse reaction is judged *reportable on an expedited basis*, it is recommended that the blind be broken only for that specific participant by the Sponsor-Investigator even if the investigator has not broken the blind. In the case of a SUSAR, the DSMC may be involved to ensure that the study team remains blinded.

If the blind must be broken for a participant, the case should be unblinded only to a limited number of people and access to the case should be limited so that the blind can be maintained as much as possible. It is also recommended that, when possible and appropriate, the blind be maintained for those persons responsible for the analysis and interpretation of results at the study's conclusion.

Reporting of the event will be followed according to FDA and local IRB guidelines depending upon the details of the specific event.

14.0 STUDY MANAGEMENT

14.1 Investigator Files and Retention of Documents:

The investigator must prepare and maintain adequate and accurate case histories designed to record all observations and other data pertinent to the study for each research participant. This information enables the study to be fully documented and the study data to be subsequently verified. Original source documents supporting entries in the case report forms include but are not limited to hospital records and clinic charts, laboratory and pharmacy records, ECG, signed ICFs, subject diaries and pathology reports. All study-related documents must be retained for the maximum period required by applicable federal regulations and guidelines or institutional policies.

14.2 Case Report Forms:

Case report forms (CRFs) will be completed for each subject enrolled. All CRFs will be complete and accurate. The medical chart and any other clinical worksheets, procedural reports, etc. are the source of verification of the data captured into the study database.

14.3 Study Monitoring:

The study will be monitored at appropriate intervals to assure compliance to GCP and to assess the data quality and study integrity. The frequency of monitoring may vary depending on enrollment rate and the quality of data collected.

The investigator and staff are expected to cooperate and provide all relevant study documentation in detail at each site visit. The study monitor will have direct access to source data for data verification. Data verification will be conducted by comparing the data entered into the CRFs with source data.

15.0 STATISTICAL CONSIDERATIONS

15.1 Study Design/Study Endpoints:

This is a prospective randomized phase II, multi-center study. Refer to protocol Section 2 for study endpoints.

16.0 SAMPLE SIZE JUSTIFICATION AND INTERIM ANALYSIS FOR FUTILITY

In the ACOSOG Z1031 study, 16% of the patients in the letrozole alone arm had a PEPI score of 0. The sample size of this trial was determined with the assumption that 16% of the patients letrozole will have a PEPI 0 score. Assuming that addition of LEE011, either 600 mg for 21/7 scheme (Arm B) or 400mg for 28/28 scheme (Arm C), will increase the rate of PEPI 0 by 20%, and setting Type I error rate of 10% and Type II error rates at 20% (Rubinstein et al., 2005) in the final analysis with an interim analysis at 0.5 information time for futility, a sample size of 80 women in the treatment arms (40 in each arm) and 40 women in the control arm are needed to achieve 80% power in a 1-sided unpooled z-test with continuity correction for H_a : 36% vs. H_0 : 16%. This calculation was performed on nQuery + nTerim 3.0 using the O'Brian-Fleming spending function, and finds the drift parameter value of 2.224 and the futility lower bound of 0.0876.

Because the total sample size is estimated to be $80 + 40 = 120$ patients, the planned 0.5 information time for futility requires $120 \times 0.5 = 60$ patients. If the z-statistic is below the aforementioned lower bound 0.0876, the study will be stopped early for futility.

16.1 Accrual rate and study duration:

It is anticipated that 6 subjects per month will be enrolled. Accrual will be completed in 19 months. Pathology data will be available on the last subject 6 months after the accrual is complete. The trial should be completed for the primary endpoint analysis in 26 months after accrual is initiated.

16.2 Data Analysis Plans:

Although the trial is designed with 3 arms, the hypotheses concern about the comparisons of the two treatment arms combined vs. the control, hence 2-sample methods are planned.

The primary endpoint

The frequency and proportion of patients with PEPI score 0 at surgery will be reported for each arm. The 1-sided 90% confidence intervals (CI) will also be computed for the difference of proportions. The proportions will be compared between treatment (Letrozole with 2 ribociclib arms combined) and control by 1-sided unpooled z-test with continuity correction for both the interim futility and the final analyses at 0.02 and 0.094 significance level, respectively, to retain a cumulative 0.10 significance level. The trial will be stopped early if the z-value in the futility analysis is below the boundary of 0.0876.

The secondary endpoints

The secondary objectives concern about four endpoints. Among them, the three binary endpoints (Complete cell cycle arrest, pCR, cCR) will be analyzed in the same way as the primary endpoint described above but they will not be analyzed for futility.

The Ki-67 level is often skewed in its distribution and will be summarized by median and corresponding 95% CI (use e.g. the CIPCTLDF option in PROC UNIVARIATE, SAS) for each arm. The Ki-67 may take zero values and will be square-root transformed, and compared between arms by 1-sided 2-sample t-test, or by Wilcoxon rank-sum test if transformations fail to make distributions approximately normal.

The 5-year relapse-free survival and corresponding confidence interval will be estimated by Kaplan-Mayer estimator for each arm, and compared between treatment arms combined vs. control by 1-sided log-rank test.

Significance for the secondary endpoints will be assessed at 0.05 significance level.

In addition, we will explore differences between the two treatment doses by 2-sided Fisher's exact test, 2-sided t- or Wilcoxon test, and 2-sided log-rank test at 0.05 significance level.

Interim analysis

Since the patient accrual was almost complete by the time first 60 patients had complete information regarding PEPI scores, interim analysis will not be performed.

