Title	Femara (Letrozole) Plus Ribociclib (LEE011) or Placebo as Neo-adjuvant Endocrine Therapy for Women With ER+, HER2-negative Early Breast Cancer
Short Title	FELINE trial
Phase	II
Methodology	Placebo controlled randomized trial
Study Duration	26 months (Date of accrual of first subject to surgery date of last subject)
Study Center(s)	Multi-center
Objectives	To determine if ribociclib in combination with letrozole for 24 weeks as neoadjuvant endocrine therapy increases the proportion of women with PEPI score of 0 at surgery compared to patients treated with letrozole alone therefore allowing more patients excellent outcomes without chemotherapy.
Number of Subjects	120 (40 in each arm) - 6 subjects a month
Diagnosis and Main Inclusion Criteria	Stage II or III women with ER+, HER2-negative breast cancer
Study Product(s), Dose, Route, Regimen	Letrozole 2.5 mg PO daily; Ribociclib 600 mg PO daily 21 days on/7 days off; Ribociclib 400 mg continuous daily dosing.
Duration of Administration	22 weeks
Reference Therapy	Letrozole 2.5 mg (control arm)
Statistical Methodology	In the ACOSOG Z1031 study, 16% of the patients in the letrozole alone arm had a PEPI score of 0. The sample size of this trial was determined with the assumption that 16% of the patients taking letrozole will have a PEPI score of 0. Assuming that addition of ribociclib will increase the rate of PEPI 0 by 20%, 80 women in the two treatment arms (B+C) and 40 women in the control arm (A) are needed to show significance.

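### Section 16 prints the drift and accrual time of a 114-patient design beside a stated need for 120, and its 80% power belongs to an interim design since dropped; the trial is not underpowered

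*Combined protocol and SAP*

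**What the plan says.** - **Size and power.** Section 16.0 states that 80 women on ribociclib (two arms of 40) and 40 controls "are needed to achieve 80% power in a 1-sided unpooled z-test with continuity correction", for 36% against 16%. The overall one-sided error is 10%, with one futility look at half the information and O'Brien-Fleming spending.
- **Software output.** The same paragraph adds "and finds the drift parameter value of 2.224 and the futility lower bound of 0.0876". The interim is placed at 60 patients, half of 120.
- **Nominal levels.** Section 16.2 tests at 0.02 (interim) and 0.094 (final), to keep 0.10 overall, and reports a one-sided 90% confidence interval.
- **Accrual.** Section 16.1 expects 6 patients per month and says "Accrual will be completed in 19 months". Pathology on the last patient follows 6 months later, and the total is 26 months. The Study Summary gives "120 (40 in each arm) - 6 subjects a month" and the same 26 months.
- **Interim dropped.** The last paragraph of Section 16.2 says that "interim analysis will not be performed", because accrual was nearly finished before the first 60 patients had PEPI data.

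**The concern.** The drift and the accrual time each look like a small slip. They point to the same number, though: both fit 114 patients, and the text says 120. Nothing in Section 16 explains a step from 114 to 120, and no dropout allowance is stated there. A reader cannot tell whether 120 is the calculated size, a rounding up, or 114 plus an unstated margin. The difference matters if some women have no PEPI score, because only in the last case was that loss planned for.

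Separately, the only power figure in the plan is for a two-look design that will not be carried out. The plan gives no power for the single analysis that will be done. It also leaves open whether that analysis is at 0.094, a level that exists only because some error was set aside for the interim, or at 0.10.

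**Working it through.** **Inputs.** Rates 16% and 36%, 2:1 allocation, one-sided overall error 0.10, type II error 0.20, one look at information 0.5, O'Brien-Fleming-type spending, unpooled z with continuity correction (all Section 16.0). Accrual of 6 per month, 19 months, 6-month lag and 26-month total (Section 16.1).

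**1. Reproduce the plan's own design figures.** The spending function f(e) = 2[1 − Φ(z(1−e/2)/√0.5)] gives:
- error spent at the interim, f(0.10) = 0.0200 (plan: 0.02);
- final nominal level, so that the two looks total 0.10: 0.0940 (plan: 0.094);
- type II error spent at the interim, f(0.20) = 0.0699, with normal quantile −1.476;
- drift required for exactly 80% power, with non-binding futility: 2.2117;
- futility bound = 2.2117 × √0.5 − 1.476 = 0.0876 (plan: 0.0876).

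All three printed design values are recovered, so the method is correctly identified.

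**2. Drift by sample size.** With n_T = 2n_C,

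drift = [0.20 − 0.5(1/n_C + 1/n_T)] / √(0.16·0.84/n_C + 0.36·0.64/n_T)

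| Total | n_T + n_C | Numerator | Standard error | Drift |
|---|---|---|---|---|
| 111 | 74 + 37 | 0.17973 | 0.08213 | 2.188 |
| 114 | 76 + 38 | 0.18026 | 0.08105 | 2.224 |
| 117 | 78 + 39 | 0.18077 | 0.08000 | 2.260 |
| 120 | 80 + 40 | 0.18125 | 0.07899 | 2.294 |

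The smallest 2:1 size with drift of at least 2.2117 is 114, and its drift is the printed 2.224. Other variance choices at 120 do not give 2.224 either: pooled with correction 2.056, pooled without 2.268, unpooled without 2.532.

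**3. Two-look power with the printed bounds** (0.0876; 0.02/0.094): 80.3% at 114 and 82.2% at 120.

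**4. Single-look power.** The normal value is Φ(drift − z(1−α)). The exact value sums binomial probabilities over all tables that the planned test rejects.

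| Total | Final level | Normal | Exact |
|---|---|---|---|
| 120 | 0.10 | 84.4% | 83.5% |
| 120 | 0.094 | 83.6% | 82.5% |
| 111 | 0.10 | 81.8% | 80.5% |
| 108 | 0.10 | 80.8% | 79.3% |

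On the exact basis, a single look at 0.10 first passes 80% at 111 patients.

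**5. Accrual.** 19 × 6 = 114, and 120 / 6 = 20 months. Then 20 + 6 = 26, the stated total, whereas 19 + 6 = 25.

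**The case against.** The strongest reply is that this is bookkeeping. The figure of 120 is stated consistently, the 60-patient interim is half of 120 (half of 114 is 57), and the 26-month total fits 120. Since 120 exceeds the calculated minimum, the promise of 80% power is kept. Drift enters no decision rule, and with accrual almost complete the accrual forecast guides nothing. The cancelled interim is disclosed with its reason. All of this stands, and it limits the point to documentation.

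It might also be said that 120 has a legitimate source. A fixed-design pooled formula with continuity correction, at one-sided 0.10 and 80% power, gives 39.35 controls, hence 40 + 80 = 120. A margin of about 5% would also link the sizes (114 / 0.95 = 120). But the first is neither the test nor the design that Section 16.0 names, and the second is stated nowhere. Either may be the true history; the plan does not say.

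Three stronger readings are tempting, and the documents do not support them:
- **That the trial is underpowered or its size miscalculated to its harm.** The figures err on the safe side.
- **That the bound 0.0876 is a further error, because drift 2.224 would give about 0.096.** The bound follows from the target drift 2.2117, and 2.224 is the drift after rounding up to whole patients. One software run can produce both.
- **That the whole timeline is wrong.** Only the 19-month figure is out, by one month.

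**Conclusion.** The point holds as a correctable inconsistency in the primary sample-size justification. By the stated method 114 patients are needed, not 120; the printed drift belongs to 114 (2.224 against 2.294); and accrual of 120 takes 20 months, not 19. The stated 80% power and the 0.02/0.094 split describe a two-look trial that Section 16.2 has replaced with a single look. At 120, power is 82.2% as designed with two looks, and 82.5% to 84.4% with one. The validity of the comparison is not affected.

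These figures assume the plan's 36% and 16%, a PEPI result for all 120 women, and non-binding futility with 0.02 of error spent at the interim. That last combination is the one that reproduces 0.02, 0.094 and 0.0876 together.

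**What to change.** 1. In Section 16.0, state that the calculated minimum was 114 (76 + 38, drift 2.224, 80.3%) and why 120 are enrolled. Alternatively, give drift 2.294 for 120. If 120 includes an allowance for women without a PEPI score, say so and give its size.
2. In Section 16.1, change accrual to 20 months; the 26-month total can stay.
3. Remove the futility rule from Sections 16.0 and 16.2 and the 0.02 interim level from Section 16.2, keeping the sentence that explains why no interim was done.
4. Before unblinding, fix one final one-sided level and give its single-look power at 120. The options are 0.10 (83.5% exact, 84.4% normal), which matches the intended overall error and the one-sided 90% interval, or 0.094 (82.5% exact, 83.6% normal), which is the level now written.

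Items 1 to 3 are wording. Item 4 is more than wording if 0.10 is chosen: it moves the rejection threshold of the primary test, and should be declared as a change made because no interim was performed. No extra patients or data are needed.
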